4.1.2 Dose Escalation Phase

The goal of the **Dose Escalation Phase** is to initially characterize the safety and tolerability of MGA271 and pembrolizumab administered in combination, and more specifically to describe the DLTs for each dose level studied and to define the MTD or MAD (if no MTD is defined) based on the frequency of occurrence of DLTs in each cohort. Patients with mesothelioma, urothelial cancer, NSCLC, SCCHN, ccRCC, ovarian cancer, melanoma, thyroid cancer, TNBC, pancreatic cancer, colon cancer, soft tissue sarcoma, or prostate cancer will be enrolled in the Dose Escalation Phase.

For the purposes of guiding decisions regarding dose escalation, the **DLT Evaluation Period** is defined as the time following administration of the first dose of pembrolizumab to the day of the third planned administration of pembrolizumab (i.e., Cycle 1/Initial Tumor Assessment Cycle).

Dose escalation will follow a conventional 3+3+3 design: MGA271 will be evaluated in sequential escalating doses ranging from 3 mg/kg to 15 mg/kg in combination with 2 mg/kg pembrolizumab in cohorts of 3 to 9 patients each. Dose levels of MGA271 to be evaluated include 3 mg/kg (starting dose), 10 mg/kg, and 15 mg/kg. If it is determined that the MTD is exceeded in the first dose cohort, a dose de-escalation cohort to evaluate a lower dose of MGA271 (1 mg/kg) in combination with 2 mg/kg pembrolizumab will be enrolled.

Table 3 MGA271 Dose Escalation Cohorts

Cohort	MGA271 Dose	Pembrolizumab Dose	MGA012
Cohort 1 ^a	1 mg/kg	2 mg/kg	N/A
Cohort 1	3 mg/kg (starting dose)	2 mg/kg	N/A
Cohort 2	10 mg/kg	2 mg/kg	N/A
Cohort 3	15 mg/kg	2 mg/kg	N/A
Cohort 4	15 mg/kg	N/A	375 mg

a To be evaluated only if the starting dose is determined to exceed the MTD.

An intermediate dose of MGA271 may be explored selectively during the dose escalation portion of the study, based on review of the cumulative safety, efficacy, and/or PK data on the respective arms and based upon agreement between the investigators and the Sponsor as follows:

- If Cohort 2 exceeds the MTD the following dose level may be evaluated:

- Cohort 1a: 7 mg/kg MGA271 + 2 mg/kg pembrolizumab (n=3-9 patients)
- If Cohort 3 exceeds the MTD the following dose levels may be evaluated:
 - Cohort 2a: 12 mg/kg MGA271 + 2 mg/kg pembrolizumab (n=3-9 patients)

Any escalation cohort, not exceeding the MTD, can be expanded to a maximum of 15 patients for further evaluation of safety and efficacy.

The MTD for MGA271 will be defined as the dose level at which < 33% of patients experience a drug-related DLT during the DLT evaluation period. If no MTD is defined for the combination of MGA271 and pembrolizumab after escalation to the maximum protocol-specified dose, that dose level will be designated as the MAD. Dose limiting toxicities are defined in [Section 4.2](#) and Dose Escalation Rules described in [Section 4.3](#).

Beginning with Amendment 5, a new cohort, Cohort 4, will be added to explore safety and tolerability of MGA271+MGA012 administered in combination. Since MTD was not reached for the MGA271+pembrolizumab cohorts, 15 mg/kg was determined as the maximum administered dose (MAD) for MGA271. Patients will receive 15 mg/kg MGA271 (MAD) in combination with a flat-dose of 375 mg MGA012, with both study drugs administered on a Q3W schedule (see [Table 3](#)).

For the purposes of guiding decisions regarding dose escalation, the **DLT Evaluation Period** is defined as the time following administration of the first dose of MGA271 plus MGA012 to the day of the third planned administration of MGA012 (i.e., Cycle 1 /Initial Tumor Assessment Cycle).

Enrollment in Cohort 4 will follow a conventional 3+3+3 design with decision rules as outlined in [Section 4.3](#). If the 15 mg/kg MGA271 + 375 mg MGA012 combination dose is deemed tolerable, additional patients may be added for up to a total of 15 dose evaluable patients in the cohort. No higher doses of the combination are planned. If the 15 mg/kg MGA271 +375 mg MGA012 combination dose level is found to exceed the MTD, de-escalation to 10 mg/kg MGA271+375 mg MGA012 may be explored and if that dose level were to exceed the MTD, a further de-escalation to 3 mg/kg MGA271+375 mg MGA012 may be explored following the same conventional 3+3+3 design. Any of these dose levels, not exceeding the MTD, can be expanded up to a maximum of 15 patients for further evaluation of safety and efficacy.

4.1.3 Cohort Expansion Phase

During the Cohort Expansion Phase, additional cohorts of patients with unresectable, locally advanced or metastatic melanoma (up to n=16), 2 cohorts of NSCLC (up to n=20 in each cohort), 2 cohorts of SCCHN (up to n=20 in each cohort) or urothelial cancer (up to n=16) will be enrolled to receive MGA271 in combination with pembrolizumab at the MTD (or MAD) established from the Dose Escalation Phase of the study. The goals for this portion of the study will be to:

1. Further characterize the safety MGA271 in combination with pembrolizumab at the MTD (or MAD);
2. Further evaluate the PK, PD, and immunogenicity of MGA271 in combination with pembrolizumab; and
3. Provide a preliminary assessment of the antitumor activity of MGA271 in combination with pembrolizumab in patients with advanced melanoma, NSCLC, SCCHN, or urothelial cancer.

4.1.4 Efficacy Follow-up Period

The **Efficacy Follow-up Period** consists of the 6-month (24-week) period following the final dose of study drug (pembrolizumab or MGA271 or MGA012, whichever is last) where patients will be followed for survival via telephone or other electronic contact at 12-week intervals from the start of the period. Patients who discontinue study treatment for a reason other than progressive disease may be followed for efficacy and survival until 1 of the following occurs: the patient progresses, withdraws consent for follow up, or initiates other anti-cancer therapy, or the overall trial is closed.

4.2 Dose Limiting Toxicity

For the purposes of safety management and defining DLTs, the combination of MGA271 and pembrolizumab, or the combination of MGA271+MGA012 will be treated as one entity. If a DLT is considered related to study drug, no distinction will be made as to which agent is the causative agent and administration of both agents will be stopped. One exception to this rule will be in the circumstance in which a DLT occurs during or immediately following the first pembrolizumab infusion or MGA012 infusion and before the first MGA271 administration. In this case, the toxicity will be attributed to pembrolizumab or MGA012 alone and will not count as a DLT of the combination of study drugs; in this case the patient will be replaced by another patient in the dose cohort.

In general, for patients who experience an AE that may meet the criteria for a DLT, subsequent administration of the study drugs should be held pending management and/or resolution of the event and assessment of attribution to the study drugs. Criteria for subsequent continuation of therapy are outlined below. No dose reductions of either MGA271 or pembrolizumab or MGA012 are allowed during the study.

Dose limiting toxicities will be based on treatment-emergent drug-related AEs (or laboratory abnormalities) occurring during the DLT Evaluation Period (defined as the time following administration of the first dose of pembrolizumab to the day of the third planned administration of pembrolizumab [i.e., Cycle 1/Initial Tumor Assessment Cycle.]) The severity of AEs will be graded according to the National Cancer Institute (NCI) Common Terminology Criteria for Adverse Events (CTCAE) version 4.03.

Dose limiting toxicities are defined separately for hematologic and non-hematologic events as outlined below.

4.2.1 Hematologic Dose Limiting Toxicity

Hematologic DLT will be defined as follows:

- Grade 4 neutropenia lasting > 5 days
- \geq Grade 3 febrile neutropenia lasting > 48 hours or any \geq Grade 3 febrile neutropenia associated with hemodynamic compromise or objective evidence of infection
- Grade 4 thrombocytopenia, irrespective of duration
- Grade 3 thrombocytopenia associated with clinically significant bleeding
- \geq Grade 3 hemolysis

The following events will be specifically **excluded** from the definition of hematologic DLT

- \geq Grade 3 lymphopenia
- Grade 3 anemia that is not associated with other clinically significant complications

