2.3.1.1 Safety

2.3.1.1.1 Nonclinical Data

2.3.1.1.2 Clinical Trial Experience

MGA271 is currently being evaluated in patients with cancer in 4 ongoing, Phase 1, MacroGenics-sponsored clinical studies. Clinical trial experience is presented for MGA271+pembrolizumab combination therapy for the current study (CP-MGA271-03) and MGA271 monotherapy for Study CP-MGA271-01. Data from remaining 2 studies are not included, 1 explores MGA271 treatment in a pediatric population and the other explores combination MGA271 and ipilimumab treatment.

Safety

As of the cutoff date of 13 April 2019, safety data are available for 133 patients exposed to MGA271+Pembrolizumab in Study CP-MGA271-03 and for 179 patients exposed to MGA271 in Study CP-MGA271-01. A discussion of safety for each study is presented below.

Study CP-MGA271-03

Adverse events considered related to MGA271+pembrolizumab treatment were reported in 116 patients (87.2%). The most common treatment-related adverse events (TRAEs) reported in $\geq 5\%$ of patients exposed to MGA271+pembrolizumab in decreasing order of frequency were as follows: infusion-related reaction (54.1%); fatigue (27.8%); nausea (9.8%); pyrexia (9.0%); lipase increased (8.3%); arthralgia (7.5%); events of diarrhea, rash maculo-papular, and decreased appetite (6.8%, each); events of hypothyroidism and pneumonitis (6.0%, each); events of chills, anemia, lymphocyte count decreased, and pruritus (5.3% each). Greater than or equal to Grade 3 TRAEs were reported in 38 patients (28.6%). Of these, the most commonly reported in $\geq 5\%$ of patients was infusion-related reaction (6.8%) and lipase increased (6.0%).

Forty-eight patients (36.1%) experienced at least 1 serious adverse event (SAE). The most common SAEs, reported in $\geq 2\%$ of patients in decreasing order of frequency were: infusion-related reaction (6.8%), pneumonitis (4.5%), and dyspnea (2.3%). Twenty-three patients (17.3%) experienced SAEs considered related to MGA271+pembrolizumab; the majority of these events were \leq Grade 3 in severity (20/23 patients [87%]). The most common SAEs considered related were infusion-related reaction (6.8%) and pneumonitis (4.5%). Fourteen patients (10.5%) experienced at least 1 \geq Grade 3 SAE that was considered related to MGA271+pembrolizumab; with the exception of infusion-related reaction (6 patients [4.5%]) and pneumonitis (3 patients [2.3%]), the events were singularly reported.

Study CP-MGA271-01

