4.2.2 Non-Hematologic Dose Limiting Toxicity

Non-hematologic DLT will be defined as any \geq Grade 3 non-hematologic event **with the following exceptions:**

- Grade 3 electrolyte abnormality that lasts less than 72 hours, is not otherwise associated with clinical complications, and responds to medical intervention
- Grade 3 fever that lasts < 72 hours and is not associated with hemodynamic compromise
- Grade 3 nausea or vomiting that lasts < 72 hours and responds to medical intervention
- Grade 3 amylase and/or lipase elevation that is not associated with either clinical or radiographic evidence suggestive of pancreatitis

- Grade 3 gastrointestinal AEs of diarrhea, constipation, abdominal pain, cramping, dyspepsia or dysphagia that resolves to \leq Grade 1 within 14 days with medical therapy
- Grade 3 fatigue that lasts < 7 days
- Grade 3 infusion-related reaction or cytokine release syndrome that lasts < 12 hours and responds to medical intervention.
- Grade 3 or 4 endocrinopathy that is adequately controlled with hormone supplementation
- Grade 3 skin toxicity that resolves to \leq Grade 2 within 14 days of initiation of oral corticosteroids
- Grade 3 inflammatory reaction (e.g., with associated pain, swelling) attributed to a local antitumor response (e.g., inflammatory reaction at sites of metastatic disease, lymph nodes, etc.) that resolves to \leq Grade 2 within 7 days.

Note: The following Grade 2 or greater non-hematologic AE may also be considered as DLT:

- Grade 2 AEs that are prolonged inordinately, based upon the medical judgment of the Investigator, and/or lead to permanent discontinuation of MGA271 due to patient intolerance.
- Any hepatic laboratory abnormalities meeting all three Hy's law criteria (described within **Section 4.2.3** below).
- Any Grade 2 eye pain or reduction in visual acuity that does not respond to topical therapy and does not improve to Grade 1 within 14 days of the initiation of topical therapy, or that requires systemic treatment.

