- If 2 or more patients out of the first 6 patients treated at a given dose level experience **the same** drug-related DLT, then the enrollment in that cohort will stop, and it will be concluded that the MTD for MGA271 / pembrolizumab or MGA271/MGA012 has been exceeded and all subsequent patients will be treated at the next lower dose level.
- Note that in the circumstance in which a DLT occurs during or immediately following the first pembrolizumab or first MGA012 infusion and before the first MGA271 administration, the toxicity will be attributed to pembrolizumab or

MGA012 alone and will not count as a DLT of the combination of study drugs at the dose level under study. In this case the patient will be replaced by another patient in the dose cohort.

Following these rules for dose escalation, the MTD/MAD will be the highest dose administered during the Dose Escalation Phase of the study at which the incidence of DLT is < 33%.

Dose escalation to the next dose level is permitted only after the patients enrolled in the current dose cohort have completed the DLT evaluation period and all safety data have been reviewed by the Sponsor Medical Monitor and the Investigators participating in the study.

For patients being treated at a dose level subsequently determined to exceed the MTD, the dose of MGA271 will be immediately reduced to the next lower MGA271 dose level.

At the discretion of the Sponsor, dose escalation may be stopped before an MTD is reached. In this case, the MAD may be chosen based on an assessment of PK, PD, biomarker, safety, and response data. An MTD does not have to be reached to expand a dose cohort if the available data demonstrate that a lower dose level may provide antitumor activity while minimizing potential risk.

At the discretion of the Sponsor, any escalation cohort at a dose level not exceeding the MTD may be expanded to a maximum of 15 patients for further evaluation of safety and efficacy. For the MGA271 + MGA012(Cohort 4), the cohort may be expanded up to a total of 15 patients.

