4.5 Guidelines for Dose Modification

No intra-patient dose escalation will be allowed. No dose reductions will be allowed with exception of 1) reduction of infusion rate during re-challenge for patients experiencing an infusion reaction ([Section 6.5.1](#)) or 2) reduction of dose in patients receiving MGA271 at a dose that is subsequently determined to exceed the MTD ([Section 4.3](#)). For patients who experience DLT that is considered related to either study drug, no further pembrolizumab or MGA271 or MGA012 will be administered.

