4.5.1 Dose Delays

Patients who experience toxicity that is potentially dose-limiting should have study drug held pending assessment, management and resolution of the toxicity. For patients in whom the toxicity is assessed to be unrelated to study drug or for whom the toxicity does not meet the criteria for DLT, therapy may be re-instituted at the same dose and schedule that was administered prior to the event, presuming the toxicity has resolved to \leq Grade 1 in severity. Reinstitution of therapy shall be conducted as follows:

For patients in whom the toxicity is assessed to be related to study drug, dose interruptions of up to 14 days are allowed for drug related toxicity. This may include up to one missed dose of pembrolizumab and up to 2 consecutively missed doses of MGA271. For the MGA271+MGA012 combination, Cohort 4, this would allow for a maximum of one dose each of MGA271 and MGA012. The procedures at the original scheduled missed visit should be performed as soon as possible with treatment reinstated as if no delay had occurred, picking up at the day where the interruption occurred, and patients receive the full complement of pembrolizumab and MGA271 or MGA271+MGA012 or as outlined in The Time and Event Schedule ([Appendix 1](#)). Patients with infusion delays $>$ 14 days due to drug related toxicity will discontinue both study drugs, complete the End of Treatment visit, and then enter the Efficacy Follow-up Period.

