5.3 Withdrawal of Patient from the Trial or Study Drug

5.3.1 Guidelines for Permanent Discontinuation

Patients who meet the following criteria should be permanently withdrawn from study therapy. Patients will continue to be followed as appropriate and consistent with protocol guidelines, but should receive no further study therapy with MGA271 or pembrolizumab or MGA012.

- The patient experiences adverse events that necessitate discontinuation of either study drug.
- The Investigator assesses that the patient's safety is adversely impacted by continuing study therapy.
- Uncontrolled intercurrent illness unrelated to cancer that renders continuing study treatment unsafe or regular study visits impossible.
- The Sponsor, Investigator, or Regulatory Agency terminates the study.
- The patient requests to be discontinued from the study, i.e. withdraws consent.
- Noncompliance with study medication or protocol-required evaluations.
- The patient exhibits progression of disease [according to irRC (i.e., irRECIST)].
- If the patient becomes pregnant during the study, the patient must discontinue study treatment immediately. Reports of pregnancy will be requested until delivery or termination in order to monitor the pregnancy outcome.
- A violation of enrollment criteria or other significant protocol violation is discovered after a patient has been enrolled and treated such that continued treatment would not be in the best interests of the patient.

If the Investigator decides that the patient should be withdrawn from the study or from dosing for any reason other than disease progression, the Sponsor or its designee must be alerted within 24 hours via an Immediately Reportable Event form ([Section 7.9](#)).

Patients who withdraw before Study Day 42 for a reason unrelated to drug toxicity may be considered to have inadequate data to support dose escalation. In this case, replacement patients may be enrolled in the same dose level.

Procedures for handling patients who fail to appear for study visits and criteria regarding when to consider patients lost-to-follow-up will be defined in the Study Procedures Manual.

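### The hematologic DLT list has no anemia entry, so non-hemolytic Grade 4 anemia and some complicated Grade 3 anemia go uncounted, although the exclusion wording implies they should count

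*Protocol*

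**What the plan says.** Section 4.2 of the protocol defines DLTs separately for hematologic and non-hematologic events. Section 4.2.1 opens with "Hematologic DLT will be defined as follows" and lists five items:

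- Grade 4 neutropenia beyond 5 days
- qualifying febrile neutropenia
- Grade 4 thrombocytopenia of any duration
- Grade 3 thrombocytopenia with significant bleeding
- hemolysis of Grade 3 or higher

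Two exclusions follow: lymphopenia of Grade 3 or higher, and "Grade 3 anemia that is not associated with other clinically significant complications". The synopsis repeats both lists.

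Section 4.2.2 makes any non-hematologic event of Grade 3 or higher a DLT, with exceptions, and adds a discretionary note that begins "The following Grade 2 or greater non-hematologic AE may also be considered as DLT". The SAP refers to DLTs but does not define them.

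The DLT count drives the 3+3+3 decisions in section 4.3. A DLT also ends treatment for the individual patient (section 4.4, and section 4.5: "For patients who experience DLT that is considered related to either study drug, no further pembrolizumab or MGA271 or MGA012 will be administered").

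**The concern.** The list and the exclusion do not fit together. Excluding only uncomplicated Grade 3 anemia leaves Grade 4 anemia and complicated Grade 3 anemia over, yet the list never picks them up. The list does contain the matching pair for thrombocytopenia: Grade 4 regardless of duration, and Grade 3 with a clinical consequence. The anemia pair looks like a drafting omission.

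DLT is part of both primary objectives. On a literal reading of the list:

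- One such event in the first three Cohort 4 patients reads as 0 of 3 rather than 1 of 3. The three further patients that section 4.3 requires after one DLT are then not required by the rule.
- Two such events in the first six patients do not trigger the stop for two patients with the same DLT.
- The individual stopping rules in sections 4.4 and 4.5 do not apply. Under section 4.5.1 the patient may restart at the same dose and schedule once the toxicity is Grade 1 or lower. Section 6.8 permits red-cell transfusion, so a transfused patient might reach that level quickly.

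Two sites could also classify the same event differently, one following the list and the other following what the exclusion implies.

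**Working it through.** **Text check.** The plan states no figure to reproduce, so the first step is to ask whether any route makes each kind of severe, drug-related anemia a DLT.

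| Event | Route to DLT | Counted? |
|---|---|---|
| Uncomplicated Grade 3 anemia | Explicitly excluded (4.2.1) | No, by design |
| Hemolytic anemia | Hemolysis item, Grade 3 or higher (4.2.1) | Yes |
| Grade 3 anemia with a complication that is itself a non-hematologic DLT | Catch-all or discretionary note (4.2.2) | Yes, or at discretion, through the complication |
| Grade 3 anemia with other clinically significant complications | None | No |
| Non-hemolytic Grade 4 anemia without such a complication | None | No |

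Lymphopenia is also excluded without being listed, so an exclusion alone does not prove that an inclusion was intended. But the lymphopenia exclusion covers every grade from 3 up and leaves nothing over. The anemia exclusion is limited both by grade and by absence of complications. Neither limit has any effect unless the remainder was meant to count.

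**How often.** Inputs are from section 2.3.1.1.2 (this study, 133 patients on MGA271 plus pembrolizumab).

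- Related anemia of any grade: 5.3%, that is 7/133.
- Related SAEs of Grade 3 or higher: "with the exception of infusion-related reaction (6 patients [4.5%]) and pneumonitis (3 patients [2.3%]), the events were singularly reported". Hence at most one patient had a related Grade 3 or higher anemia SAE: 1/133 = 0.75%, Clopper-Pearson 95% CI 0.02% to 4.12%.

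For a per-patient rate p, the chance of at least one event in n patients is 1 − (1 − p)^n. The chance of two or more in three is 3p²(1 − p) + p³.

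| | p = 1/133 | p = 4.12% |
|---|---|---|
| At least one in 3 | 1 − (132/133)³ = 2.2% | 1 − 0.9588³ = 11.9% |
| At least one in 9 | 1 − (132/133)⁹ = 6.6% | 1 − 0.9588⁹ = 31.5% |
| Two or more in 3 | 0.02% | 0.5% |

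**Effect on the dose decision.** Let b(x) be the binomial probability of x DLTs in three patients at total DLT rate t. Section 4.3 declares the MTD exceeded at 2 or more of 3, 3 or more of 6, or 3 or more of 9. Ignoring the same-DLT rule:

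P(exceeded) = [b(2) + b(3)] + b(1)[b(2) + b(3)] + b(1)²[1 − b(0)]

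Assume, for illustration, a 10% rate of other counted DLTs. Then b(0) = 0.729, b(1) = 0.243 and b(2) + b(3) = 0.028, so P = 0.028 + 0.0068 + 0.0160 = 5.1%. If anemia is counted and independent, t = 0.10 + 0.90p:

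| Anemia rate p | t | P(exceeded) |
|---|---|---|
| Not counted | 10.0% | 5.1% |
| 1/133 | 10.7% | 5.9% |
| 4.12% | 13.7% | 10.0% |

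At the observed ceiling the decision probability barely moves; at the upper limit it about doubles. At the boundary one event decides the outcome: 2/9 = 22.2% is below the 33% limit and 3/9 = 33.3% is not.

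**The case against.** The strongest counter-argument concerns consequence. Cohort 4 has no higher dose to escalate to. The synopsis says further patients will be added, up to 15, if the dose is deemed tolerable (section 4.1.2 says may). So after 0 of 3 or 1 of 3 the likely next step is the same: more patients at the same dose. This stands, and it weakens the point about the three extra patients. It does not repair the DLT count, the same-DLT stop or the individual stopping rules.

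Safeguards also exist. Dose escalation requires that "all safety data have been reviewed by the Sponsor Medical Monitor and the Investigators participating in the study". Under section 4.5.1, "dose interruptions of up to 14 days are allowed for drug related toxicity", and a longer delay stops both drugs. Section 5.3.1 ends therapy when "The patient experiences adverse events that necessitate discontinuation of either study drug". SAEs reach the sponsor within 24 hours. These protect patients in practice, but none of them changes which events count as a DLT.

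It can also be argued that leaving anemia out was deliberate: eligibility sets platelet and neutrophil floors but no hemoglobin floor, and transfusion is allowed. The documents do not say this. If it was the intention, the qualified exclusion is misleading and still needs correction. A related argument, that an investigator could read the exclusion as making Grade 4 anemia a DLT, concedes the ambiguity.

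Finally, 1/133 is already a ceiling. It may include hemolytic or uncomplicated Grade 3 cases, and a confidence limit placed on a ceiling is pessimistic. That is fair; the 11.9% and 31.5% are outer bounds. In the other direction, a Grade 4 value judged non-serious would escape an SAE count.

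**Conclusion.** The concern holds. As written, the DLT definition leaves out drug-related non-hemolytic Grade 4 anemia, and Grade 3 anemia whose complications are not themselves DLTs, while its own exclusion implies that they count. The rule misclassifies a primary-endpoint event, and it should be fixed.

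The practical size is small: roughly a 2% chance of such an event in the first three patients and 7% in nine. These figures assume that the rate of at most 1/133 carries over to Cohort 4. That rate comes from a different anti-PD-1 combination with weekly MGA271, covers all treatment rather than the 6-week DLT window, and counts serious events only.

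The reach is limited too. The pembrolizumab cohorts are closed and the 15 mg/kg MAD is set, so the prospective effect is on Cohort 4 and any de-escalation from it. The documents do not say whether any Cohort 4 DLT window is still open.

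**What to change.** Add two entries to the hematologic DLT list in section 4.2.1 and in the synopsis: Grade 4 anemia; and Grade 3 anemia associated with clinically significant complications. Keep the exclusion of uncomplicated Grade 3 anemia as it stands. Optionally, check the closed pembrolizumab cohorts for anemia of these kinds within the DLT window.

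The cost is two short lines in two places. The downside is that an occasional anemia event will count as a DLT, adding three patients to a cohort or ending one patient's treatment.
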